# 3.2.2 Efficacy

All efficacy analyses for the fixed dose Treatment Cycle 1 will be performed on the mITT population. Assessment of repeat efficacy by Treatment Cycle will only include subjects who received the treatment in the designated Treatment Cycle. The primary and secondary efficacy analyses (designated efficacy parameters at Week 6 of the fixed dose Treatment Cycle 1) will also be performed on the PP population. Efficacy tables will be presented by treatment group of the Study Limb Dose, see Section 3.2.1.1.

Baseline will be defined as the last measurement collected prior to receiving the initial study treatment in Treatment Cycle 1 on Day 1. MAS score, CC

may also have been measured in muscle groups other than those injected. Only assessments from subjects who received treatment in the respective muscle group will be included in the analyses.

In addition to the analyses described below, descriptive statistics will be provided for all efficacy endpoints.

34/108

3.2.2.1 Primary Efficacy Analysis

The primary efficacy endpoint is the mean change from Baseline to Treatment Cycle 1, Week 6 in MAS score in the Treatment Cycle 1 PTMG (elbow flexors or wrist flexors).

The primary efficacy endpoint will be analysed using an Analysis of Covariance (ANCOVA) on the rank of the mean changes. This model will include treatment group, the baseline value, the two stratification factors (age range and BTX treatment naïve status at baseline) and the pooled centre as fixed covariates.

For handling of multiplicity see section 3.1.5.

Adjusted means (LS Means) together with their standard error (SE) and 95% confidence interval (CI) will be provided for the ranked changes of each treatment group. To help interpret the results the LS mean rank values will be back transformed to the original (derived) scale. The LS means on the original scale will be presented as well as the estimate of the magnitude of the back transformed difference between the treatment groups (for any of the two tested doses of Dysport (8 U/kg and 16 U/kg), the LS mean of the back transformed difference Dysport tested dose - Dysport 2 U/kg) and the associated p-values. Additionally, for all other effects taken into account in the ANCOVA the respective type III test p-value will be presented.

The following SAS® code will be used to compare the Dysport (8 U/kg and 16 U/kg) versus Dysport 2 U/kg.

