9.1.3.3 Dose/Volume by Muscle

The entire volume for injection (1.6 mL) will be injected and will be divided between the PTMG (elbow flexors or wrist flexors) and a number of additional muscles selected by the Investigator according to the disease presentation.

The volume injected into the additional muscles must not exceed that specified in the dosing paradigm in [Table 3](#). No more than 0.5 ml will be injected per injection site.

The injection volume, number of injection sites and dose by muscles in the PTMG are provided in Table 2. Those are mandatory for the PTMG at treatment 1 and should be applied at other treatment cycles if clinically indicated.

- If elbow flexors are chosen as the PTMG, both brachialis and brachioradialis have to be injected at the injection volume specified in Table 2.
- If wrist flexors are chosen as the PTMG, both flexor carpi radialis and flexor carpi ulnaris have to be injected at the injection volume specified in Table 2.

Table 2 Injection Volumes, Dose per Muscle and Number of Injection Sites in the Primary Targeted Muscle Group

For Primary Targeted Muscle Group (PTMG)	Injection Volume (mL)	Number of Injection Sites	Dose per Muscle in U/kg / Maximum U		
			Low 2 U/kg	Medium 8 U/kg ^(a)	High 16 U/kg ^(a)
Elbow flexors					
Brachialis	0.6	2	0.75 U/kg/30 U	3 U/kg/120 U	6 U/kg/240 U
Brachioradialis	0.3	1	0.375 U/kg /15 U	1.5 U/kg/60 U	3 U/kg/120 U
Wrist flexors					
Flexor carpi radialis	0.4	1 - 2	0.5 U/kg /20 U	2 U/kg/80 U	4 U/kg/160 U
Flexor carpi ulnaris	0.3	1	0.375 U/kg /15 U	1.5 U/kg/60 U	3 U/kg/120 U

^a The total dose for the study limb must not exceed 320 U in the 8 U/kg group and 640 U in the 16 U/kg group.

CCI

9.1.3.4 Dose/Volume at Treatment 2, 3 and 4

CCI
[Redacted text]

[Redacted text]

[figure not shown]
CCI [Redacted text]

[Redacted text]

[Redacted]	[Redacted]	[Redacted]
[Redacted]	[Redacted]	[Redacted]
[Redacted]	[Redacted]	[Redacted]
[Redacted]	[Redacted]	[Redacted]
[Redacted]	[Redacted]	[Redacted]
[Redacted]	[Redacted]	[Redacted]

[Redacted text]

Figure 2 Dose Modifications Available During the Study

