3.2.2.7 Subgroup Efficacy Analyses and Covariates

Covariates used in models of efficacy analysis will be the same as those mentioned in sections 3.1.1 and 3.1.2.

The model will be run including the centre effect, which will be removed if the model does not converge.

The following additional subgroup analyses will be conducted on the MAS and the PGA of the mITT population:

Primary (MAS) and First Secondary (PGA) Efficacy Endpoint

- Age group (2 to 9 years and 10 to 17 years)
- BTX status at baseline (naïve or non-naïve)
- Sex (Male or Female).

MAS and PGA at Treatment Cycle 1 Week 16

• Physiotherapy/Occupational therapy status at Week 16 (No/Yes): Subjects without physiotherapy nor occupational therapy before week 16 of Treatment Cycle 1 versus subjects with physiotherapy and/or Occupational therapy between Baseline and Week 16 of Treatment Cycle 1.

Statistical analyses will include:

- A summary table of raw values and changes from baseline to all visits, by treatment group and overall, in each subgroup separately.
- A rank ANOVA model (score= subgroup\_indicator + treatment + BTX stratum + age group + interaction subgroup \* treatment + centre) or rank ANCOVA model (change = baseline + subgroup\_indicator + treatment + BTX stratum + age group + interaction subgroup \* treatment + centre).

Following contrast analyses for reporting will be performed in case the p-value from the interaction term is deemed statistically significant (lower than 0.1):

- i. The Least Square Mean (LSMeans) of change from baseline in each subgroup, for each treatment group separately, together with its 95% CI,
- ii. Difference in LSMeans in each subgroup between each active dose and Dysport 2 U/kg, together with its 95% CI and the p-value of the test  $H_0$ :Adjusted MeanDysport (8 and 16 U/kg) = Adjusted MeanDysport 2 U/kg.

The ANOVA or ANCOVA models will only be run if there are at least 20 subjects in at least one treatment group. 20 subjects was deemed to be a reasonable number of subjects in order for the analyses to be considered to be meaningful rather than being calculated using any formal statistical methodology.

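### PTMG (elbow or wrist) decides which muscle group supplies the primary outcome, yet it is neither a term in the primary MAS models nor a listed subgroup

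*SAP*

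**What the plan says.** **Endpoint.** SAP 3.2.2.1 takes the mean change from baseline to "Week 6 in MAS score in the Treatment Cycle 1 PTMG (elbow flexors or wrist flexors").

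**Model.** SAP 3.2.2.1 specifies an ANCOVA on ranked MAS changes: "This model will include treatment group, the baseline value, the two stratification factors (age range and BTX treatment" status), "and the pooled centre as fixed covariates". The SAS code there, the centre-interaction model and POM in SAP 3.2.2.2, and Protocol 11.4.3.3 have no PTMG term either.

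**What PTMG fixes at Treatment 1.** Protocol 9.1.3.3 says "If elbow flexors are chosen as the PTMG, both brachialis and brachioradialis have to be injected" and "If wrist flexors are chosen as the PTMG, both flexor carpi radialis and flexor carpi ulnaris have to be injected". Of the Table 2 volumes, sites and doses it says "Those are mandatory for the PTMG at treatment 1".

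**When PTMG is set.** It is nominated at study entry (Protocol 4.1.3) and forms part of inclusion criterion 6 at the baseline visit (6.2). It must be the muscle group with the higher baseline MAS, with ties left to the investigator (9.1.3.2). Baseline assessments come before randomisation (7.2.2), but 9.1.3.2 ties the selection only to the time before injection.

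**Stratification and subgroups.** Randomisation is stratified by age range and BTX status only (Protocol 9.2.1). SAP 3.2.2.7 introduces its list with "The following additional subgroup analyses will be conducted on the MAS and the PGA of the mITT population" and names age group, BTX status, sex and, at Week 16, physiotherapy/occupational therapy. Protocol 11.5 does not name PTMG either.

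**Nearest related analyses.** SAP 3.2.2.5 fits a separate rank ANCOVA to MAS change in each injected muscle group. SAP 3.2.9.3 tabulates PTMG by dose group.

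**The concern.** PTMG determines which joint is scored, which muscles must be injected and what share of the limb dose they receive. If MAS change differs between elbow and wrist for reasons unrelated to arm, that difference sits in the residual of the primary model. Any chance excess of elbow targets in one arm then moves the estimate a little. A prognostic factor known before treatment can remove both effects for one degree of freedom.

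The second issue is interpretation. The plan examines homogeneity across centres and prespecifies age, BTX and sex subgroups. It gives no corresponding split of the primary endpoint by the factor that decides which muscle group is measured.

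**Working it through.** **1. The plan's own figure.** SAP 1.3.4 gives 99% power for each of the first two endpoints and 98% jointly. The product is 0.99 × 0.99 = 0.9801, which agrees. The effect size and SD behind the 99% are redacted, so that figure cannot be rebuilt. Back-solving at 70 per arm and two-sided 0.05, the implied standardised difference is (1.960 + 2.326) × √(2/70) = 0.72. At 0.025 it would be 0.77.

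**2. PTMG dose, from Table 2 (Protocol 9.1.3.3).**

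| | Volume (mL) | 2 U/kg arm | 8 U/kg arm | 16 U/kg arm |
|---|---|---|---|---|
| Elbow | 0.6 + 0.3 = 0.9 | 0.75 + 0.375 = 1.125 | 3 + 1.5 = 4.5 | 6 + 3 = 9 |
| Wrist | 0.4 + 0.3 = 0.7 | 0.5 + 0.375 = 0.875 | 2 + 1.5 = 3.5 | 4 + 3 = 7 |

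Doses are in U/kg. The elbow share is 0.9/1.6 = 56.25% and the wrist share 0.7/1.6 = 43.75%, a ratio of 9/7 = 1.29 in every arm. The ratio of tested dose to control is 4-fold and 8-fold for both targets. The absolute gaps from control are 3.375 and 7.875 U/kg for elbow and 2.625 and 6.125 U/kg for wrist. Total limb dose within an arm is the same whichever PTMG is chosen.

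**3. Precision.** If PTMG explains a fraction R² of outcome variance, adjustment multiplies the residual SD by √(1 − R²). The documents give no R², so the values below are assumptions.

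| R² | Power from 99% | Power from 80% |
|---|---|---|
| 1% | 99.1% | 80.4% |
| 2% | 99.1% | 80.8% |
| 5% | 99.3% | 82.0% |
| 10% | 99.5% | 84.0% |

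For example, at R² = 10%: 4.286/√0.90 − 1.960 = 2.558, which gives 99.5%.

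**4. Chance imbalance.** The SD of the difference in elbow share between two arms of 70 is √(2p(1 − p)/70). With p = 0.5 this is 8.5 percentage points; with p = 0.8 it is 6.8. The probability of a gap above 10 points is 24% and 14% respectively. The elbow share p is assumed.

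**5. Simulation of the rank ANCOVA.** The settings were 4,000 runs per case, 70 per arm, an assumed 60% elbow share, and baseline and treatment in the model but not age, BTX status or centre. One tested arm was compared with control at two-sided 0.05.

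| PTMG effect (latent SD) | Type I error without / with PTMG | Power without / with PTMG |
|---|---|---|
| 0 | 5.4% / 5.4% | 69.2% / 69.1% |
| 0.3 | 5.2% / 5.0% | 67.8% / 68.9% |
| 0.6 | 4.8% / 4.7% | 64.8% / 67.3% |

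The Monte Carlo standard error near 5% is √(0.05 × 0.95/4000) = 0.34 points. Type I error is therefore at its nominal level either way. The power gain appears only if PTMG is prognostic. The power scenario was deliberately set well below the plan's 99% so that a change would be visible.

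**The case against.** A good case can be made for leaving the model alone.

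- **Validity is not at stake.** Stratification factors, baseline MAS and centre are a defensible prespecified set, and randomisation protects the comparison. A reader might infer that pooling two muscle groups biases the result or inflates type I error; the simulation shows no inflation, and the documents give no ground for bias. This part of the objection stands in full.
- **The dose difference is by design.** Protocol 4.3 explains that proximal and distal muscle groups differ in bulk and may need different doses and volumes. The 1.29 ratio is therefore not evidence that outcomes differ by PTMG, and the proportional contrast with control is identical. This stands too.
- **Muscle-specific results are planned.** A reader might infer that the trial could say nothing about elbow and wrist separately. That goes too far. The tertiary models per injected muscle group include Week 6, and because PTMG injection is mandatory every child's primary outcome feeds the matching model. But those models also take in muscle groups injected at the investigator's discretion as additional targets, so they do not split the primary endpoint.
- **Imbalance will be visible.** SAP 3.2.9.3 tabulates PTMG for Cycle 1. Seeing an imbalance is not the same as adjusting for it.
- **PGA is different.** Protocol 8.1.2 rates response in the upper limb as a whole, so the argument for MAS does not carry over to the PGA models. This stands.
- **Redaction.** Some tertiary endpoints, the multiplicity section and the table index are blacked out, and Protocol 11.5 permits further subgroups on clinical grounds. A PTMG analysis may exist there. The primary model, its code and the named subgroups are visible and do not contain one.

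**Conclusion.** The point holds in a modest form. A recorded pre-treatment factor that defines which muscle group is scored is absent from the primary MAS models and from the named subgroups. The consequences are:

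- a loss of precision that is probably small and cannot be quantified from the documents, since the R² range is an assumption;
- unadjusted chance imbalance of the size shown in the working, which depends on the assumed elbow share and matters only if PTMG is prognostic;
- only partial evidence on whether the primary result is consistent across its two targets.

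The third matters most. A main-effect covariate alone would not resolve it; the interaction and subgroup analysis would. With stated power of 99%, this is a worthwhile and inexpensive improvement, not a threat to the primary conclusion.

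**What to change.** Before unblinding:

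1. Add PTMG (elbow/wrist) as a fixed factor in the MAS rank ANCOVA (SAP 3.2.2.1) and the MAS POM (SAP 3.2.2.2). Protocol 11.4.3.3 also lists the covariates, so either align it or record the change in SAP section 5.
2. Add PTMG to the SAP 3.2.2.7 subgroup list for MAS, using the treatment-by-subgroup interaction model already specified there, and to the forest plot in SAP 3.2.2.6.
3. State that the PTMG used in every analysis is the one fixed before randomisation. This closes the gap left by Protocol 9.1.3.2, notably for tied baseline scores.

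A PTMG term in the PGA models is optional.

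The cost is one model degree of freedom for the covariate, one extra subgroup analysis and the wording changes. No new data are needed, and the sample size and injection scheme are unaffected. Added after unblinding, the same analyses would be post hoc.

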## **ANCOVA model without interaction**

proc mixed data = <xxx>;

class Treatment age\_range BTX\_stratum centre; model rank\_change = Treatment baseline age\_range BTX\_stratum centre / solution cl; /\* contrast analyses \*/ estimate 'Dysport 16 U/kg versus Dysport 2 U/kg' Treatment -1 0 1/cl; estimate 'Dysport 8 U/kg versus Dysport 2 U/kg' Treatment -1 1 0/cl; /\* Adjusted means and 95% CI by treatment group \*/ lsmeans Treatment/ cl ; ods output SolutionF = SolutionF Tests3 = Tests3 Estimates = Estimates LSMeans = LSMeans;

run; quit;

3.2.2.2 Sensitivity Analyses for the Primary Efficacy Endpoint

# **Centre Effect**

In order to investigate homogeneity of treatment response across centres a sensitivity analysis will be conducted: The ANCOVA model on the rank will be rerun, adding the treatment by centre interaction term, fitted as a fixed effect. If the pvalue from the interaction term in the model is lower than 0.1 then the treatment by interaction will be deemed statistically significant and it will be concluded that the treatment effect is not constant from centre to centre. If this is the case then the influence of centre on the treatment effect will be further investigated by estimating and plotting the treatment groups differences (for any of the higher doses of Dysport, LS Mean of the rank values together with their SE and 95% CI as well as

the LS mean of the back transformed difference (8 U/kg and 16 U/kg) Dysport 2 U/kg) separately for each centre. This analysis will be performed using postpooling centres. The strategy for pooling centres has been detailed in section 3.2.16.

#### **ANCOVA model with interaction:**

proc mixed data =  $\langle xxx \rangle$ ; class Treatment BTX stratum age range centre; model rank change = Treatment baseline age range BTX stratum centre centre\*treatment / solution cl; /\* contrast analyses for centre 1 \*/ estimate 'Dysport 16 U/kg versus Dysport 2 U/kg' Treatment -1 0 1 Centre\* Treatment -1 0 1 /cl; estimate 'Dysport 8 U/kg versus Dysport 2 U/kg' Treatment -1 1 0 Centre\* Treatment -1 1 0/cl; /\* contrast analyses for centre 2 \*/ estimate 'Dysport 16 U/kg versus Dysport 2 U/kg' Treatment -1 0 1 Centre\* Treatment 0 0 0 -1 0 1 /cl; estimate 'Dysport 8 U/kg versus Dysport 2 U/kg' Treatment -1 1 0 Centre\* Treatment 0 0 0 -1 1 0/cl; . . . . /\* contrast analyses for last centre \*/ estimate 'Dysport 16 U/kg versus Dysport 2 U/kg' Treatment -1 0 1 Centre\* Treatment 0 0 0 .... -1 0 1 /cl; estimate 'Dysport 8 U/kg versus Dysport 2 U/kg' Treatment -1 1 0 Centre\* Treatment 0 0 0 .... -1 1 0 /cl; /\* Adjusted means and 95% CI by treatment group \*/ lsmeans centre\*Treatment/ cl; ods output SolutionF = SolutionF Tests3 = Tests3 Estimates = Estimates LSMeans = LSMeans: run; quit;

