11.4.3.4 Adjustment for Country/Centre Effect

For the primary efficacy endpoint only, a sensitivity analysis will be conducted in order to investigate homogeneity of treatment response across centres: the ANCOVA on the rank will be re-run, adding the treatment by centre interaction term. If the p-value from the interaction term in the model is lower than 0.1 then the treatment by centre interaction will be deemed statistically significant and it will be concluded that the treatment effect is not constant from centre to centre. If this is the case then the influence of centre on the treatment effect will be investigated by estimating and plotting the treatment groups differences (for any of the two higher doses of Dysport, least square means difference Dysport higher dose - Dysport low dose) separately for each centre.

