### 3.2.16 Pooling of Centres

It is not planned to perform a subgroup analysis on individual or groups of centres. In order to assure that the centre effect will be properly estimated in the statistical models, it is necessary to only consider the centres with a sufficient number of recruited subjects. Therefore, it has been decided to apply the following approach:

- the centres having recruited at least six subjects will be taken into account for the estimate of the centre effect.
- the centres having recruited less than six subjects will be pooled with one (or several) centre(s) within the same country (or across countries within the same region) until the number of subjects in the resulting pooled centre(s) is at least equal to six. Then, only the pooled centre(s) will be taken into account for the estimate of the centre effect.

With such an approach, all the centres (original or pooled) considered for the estimate of the centre effect will account for at least six recruited subjects.

The pooling of small centres will be confirmed at the BDRM prior to unblinding. For the primary efficacy endpoint only, a sensitivity analysis will be conducted in order to investigate homogeneity of treatment response across centres.

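### The by-centre ESTIMATE statements in the interaction ANCOVA place their coefficients on the wrong interaction columns, so none of the direct per-centre treatment differences is estimable.

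*SAP*

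**What the plan says.** SAP 3.2.2.2 (Centre Effect) re-runs the rank ANCOVA with a fixed treatment-by-centre interaction. Protocol 11.4.3.4 describes the same analysis, and both documents set the trigger for the follow-up as an interaction p-value below 0.1; in the Protocol's words, "value from the interaction term in the model is lower than 0.1". If it is met, the SAP says that "the influence of centre on the treatment effect will be further investigated by estimating and plotting the treatment groups differences", separately for each pooled centre.

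The code for this is the block headed ANCOVA model with interaction:

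- The CLASS statement reads "class Treatment BTX stratum age range centre": Treatment first, centre last. (The two stratification variables carry underscores in the primary model's code.)
- Centre 1, 16 versus 2 U/kg: "Treatment -1 0 1 Centre\* Treatment -1 0 1 /cl".
- Centre 2, 16 versus 2 U/kg: "estimate 'Dysport 16 U/kg versus Dysport 2 U/kg' Treatment -1 0 1 Centre\* Treatment 0 0 0 -1 0 1".
- Centre 2, 8 versus 2 U/kg: "Treatment -1 1 0 Centre\* Treatment 0 0 0 -1 1 0/cl".
- The last centre has its coefficients in the final three positions.
- A separate LSMEANS statement requests centre-by-treatment means with confidence limits, but no differences.

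SAP 3.2.16 pools small centres so that every centre in the model "will account for at least six recruited subjects".

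**The concern.** The ESTIMATE lines treat the interaction columns as consecutive blocks of three, one block per centre, with the arm changing fastest. The CLASS statement implies the opposite layout: all centres for the first arm, then all for the second, then all for the third. The coefficients then do not describe a treatment difference within any centre.

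These lines are the only code in the SAP that produces a per-centre treatment difference directly. If the interaction test is triggered, the prespecified follow-up would fail for every centre. Replacement code would then be written after the interaction result had been seen.

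**Working it through.** **Inputs from the documents.** CLASS order and ESTIMATE coefficients: SAP 3.2.2.2. Sample size 210: Protocol 11.3 and SAP 1.3.4. Minimum pooled centre size 6: SAP 3.2.16. Hence at most 210/6 = 35 pooled centres. The actual number, k, is not given, so k = 2 to 35 was covered.

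**Input from the software.** PROC MIXED, in the package named in SAP 4.2, lays out a crossed effect in CLASS order with the last-listed variable indexing fastest, whichever way round the effect is typed. This convention is not stated in the documents.

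**Where the coefficients land.** With arms i = 1, 2, 3 and centres c = 1 to k, the interaction column for arm i at centre c is number (i − 1)k + c. Taking the arms in the order the SAP assumes (2, 8, 16 U/kg) and k = 10:

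| ESTIMATE block | Columns used | What those columns are |
|---|---|---|
| Centre 1 | 1–3 | 2 U/kg at centres 1, 2, 3 |
| Centre 2 | 4–6 | 2 U/kg at centres 4, 5, 6 |
| Last centre | 28–30 | 16 U/kg at centres 8, 9, 10 |

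**Why no contrast is estimable.** An estimable function must be a combination of cell means. Write l(i,c) for the interaction coefficients. Two conditions follow:

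- the Treatment coefficient for arm i must equal the sum of l(i,c) over centres;
- the centre coefficient for centre c must equal the sum of l(i,c) over arms. No centre coefficients are given, so this sum must be 0.

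For 16 versus 2 U/kg, with Treatment coefficients −1, 0, 1, the −1 must therefore lie in arm 1 and the +1 in arm 3 of the same centre. Those are columns c and 2k + c, which are 2k apart. The code puts them 2 apart, which works only if k = 1. For 8 versus 2 U/kg they must be k apart; the code puts them 1 apart, again valid only if k = 1. The argument does not depend on how the three dose levels sort.

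**Numerical check.** The full design matrix was built (intercept, Treatment, baseline, age range, BTX stratum, centre, interaction) and each ESTIMATE row L was tested by rank([X; L]) = rank(X) or the equivalent generalised-inverse condition.

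| Layout | Estimable by-centre contrasts |
|---|---|
| CLASS as written, all cells filled | 0 of 2k for every k = 2 to 35 |
| CLASS as written, random allocation with empty cells (k = 10, 20, 30, 35; 100 data sets each) | 0 of 19,000 |
| CLASS as written, coefficients moved to columns c, k + c, 2k + c (k = 10) | 20 of 20 |
| Centre before Treatment in CLASS, all cells filled | 2k of 2k for every k = 2 to 35 |
| Centre before Treatment in CLASS, random allocation with empty cells dropped | 8,805 of 19,000 |

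**What still works.** At k = 5 with CLASS as written, 15 of 15 centre-by-arm LS means are estimable. With one cell empty, all 14 remaining ones are.

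**Why reordering CLASS is fragile.** If no column is created for a centre-by-arm cell without subjects, every later column moves up and the fixed positions no longer fit. At k = 5 with a single empty cell, between 0 and 5 of the 5 centre contrasts for a given dose survive, depending on which cell is empty. Assuming independent 1:1:1 allocation, a centre of n subjects lacks at least one arm with probability 3(2/3)^n − 3(1/3)^n:

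- n = 6: 192/729 − 3/729 = 189/729 = 0.259
- n = 10: 3,072/59,049 − 3/59,049 = 3,069/59,049 = 0.052

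**The case against.** The strongest objections, and what stands of each:

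- **The finding rests on a SAS rule that neither document states.** True, and if columns followed the order in which the effect is typed, the code would be right. But the rule is a property of the software the SAP specifies and can be confirmed by one run on dummy data.
- **The follow-up is not lost altogether.** This stands. A reader might infer that a triggered interaction would leave the team with no by-centre result and no plot. The documents do not support that: the LSMEANS request in the same block does not use the ESTIMATE coefficients and still gives each arm's mean rank by centre with SE and CI, as SAP 3.2.2.2 asks. Point differences can be formed from those means, back-transformed and plotted. What is missing is the direct difference with its own SE, CI and p-value.
- **It cannot mislead, and quality control would catch it.** The lines return `Non-est`, so no wrong number can pass unnoticed. The block is a template with placeholders, and SAP 4.3 requires logic checks, double programming and output review. These would expose the failure, but they do not correct the prespecified code, and a second programmer working from the same SAP would meet the same lines.
- **The empty-cell figures concern a repair the SAP does not propose.** Fair. They show only why the obvious repair is insufficient. The 26% applies at the six-subject floor. Pooled-centre sizes are not given, and part of the randomisation section (Protocol 9.2.1) is redacted, so a constraint on allocation within centre cannot be ruled out.

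**Conclusion.** The point holds as a coding error of minor weight. As written, every by-centre ESTIMATE line is non-estimable, for both dose comparisons and for any number of centres from two up. The SAP's code therefore does not deliver the direct per-centre differences that the text relies on once the interaction p-value falls below 0.1.

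It should not be read as a threat to the primary result: the primary model has no interaction term, and the interaction test is also untouched. The step at issue is a conditional sensitivity analysis.

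The conclusion assumes the PROC MIXED column convention stated above. The 26% and 5% figures further assume independent 1:1:1 allocation within centre, and the column shift assumes that empty cells generate no column.

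**What to change.** In the ANCOVA model with interaction block of SAP 3.2.2.2, delete the positional by-centre ESTIMATE statements. Obtain the 8 versus 2 and 16 versus 2 U/kg differences within each pooled centre, with SE, CI and p-value, from the centre-by-treatment LS means by a statement that does not depend on column position, such as LSMEANS with differences by slice, or a non-positional LSMESTIMATE. CLASS order then no longer matters and need not change.

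Add one sentence: where a pooled centre has no subject in one of the arms being compared, that comparison is listed as not available and is left off the plot.

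The cost is one code block and one sentence in the SAP, with a short test run on dummy data. Data collection, timelines and the primary analysis are unaffected.
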